### 8.8.3 Treatment Compliance

Treatment will be administered by the Investigator to each subject on Day 1, 8, 15 and 21 as per the treatment schedule for each of the subjects randomized to one of four groups. If a subject misses a treatment, that treatment will not be made up and subject will return for the next scheduled treatment.

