## 9 DISCONTINUATION AND LOST TO FOLLOW-UP

### 9.1 Discontinuation of Study Intervention

Discontinuation from FX-322 does not mean discontinuation from the study, and remaining study procedures should be completed as indicated by the study protocol. If a clinically significant finding is identified (including, but not limited to changes from baseline) after enrollment, the investigator or qualified designee will determine if any change in participant management is needed. Any new clinically relevant finding will be reported as an adverse event (AE).

The data to be collected at the time of study intervention discontinuation will include the following:

- All efforts will be made for the subject to complete all of the follow up visits.
- If the subject does not wish to continue the follow up period, all efforts will be made for the subject to complete all assessments collected at the last follow up visit (see Section 8.4.4).

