  - All tables that summarize results by treatment group for subjects in the Full Analysis Set (FAS) or Per Protocol Analysis Set (PPAS), defined in Section 4, will include each of the FX-322 treatment groups, a pooled FX-322 treatment group, and the placebo treatment group. Subjects in the FAS or PPAS will be classified into randomized treatment groups based on their randomized treatment.

Randomized Treatment Group	# of Subjects	Day 1	Day 8	Day 15	Day 21
FX-322 1x	24	FX-322	Placebo	Placebo	Placebo
FX-322 2x	24	FX-322	FX-322	Placebo	Placebo
FX-322 4x	24	FX-322	FX-322	FX-322	FX-322
FX-322 Pooled	72	FX-322	Placebo or FX-322	Placebo or FX-322	Placebo or FX-322
Placebo	24	Placebo	Placebo	Placebo	Placebo

- For assessments completed by ear for each subject, the unit of analysis will be the ear and treated and untreated ears will be summarized separately. Treated ears will be defined as the qualified ears for treatment that received at least one dose of study treatment per the randomized treatment schedule, and untreated ears will be the ears not qualified for treatment. For analyses by ear, the treatment group for each ear will be the subject’s randomized treatment group, regardless of actual administration in the given ear. All treated (qualified) ear data will be analyzed, including those with dosing administration errors. All untreated (not qualified) ear data will be analyzed up until any dosing administration error (wrong ear injection). For analyses by ear, data for untreated (not qualified) ears after a dosing administration error will be excluded from FAS and PPAS analyses.
- All tables that summarize results by treatment group for subjects in the Safety Analysis Set (SfAS) will include 1 FX-322 dose received, 2 FX-322 doses received, 4 FX-322 doses received, and placebo (0 FX-322 doses received). For SfAS analyses by subject, all subjects in the SfAS will be classified into actual treatment groups based on the actual number of FX-322 doses received in any ear (qualified or not qualified). In the event that any subject(s) receive 3 FX-322 doses, separate listings for subject(s) receiving 3 FX-322 doses will be created. Subjects receiving 3 FX-322 doses will be included in the total column.

Actual Treatment Group	# of Subjects Planned	Days 1-21
FX-322 1x	24	1 dose of FX-322
FX-322 2x	24	2 doses of FX-322
FX-322 4x	24	4 doses of FX-322
Placebo	24	0 doses of FX-322

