For assessments completed by ear for each subject, the unit of analysis will be the ear and treated and untreated ears will be summarized separately. An ear will be considered treated from the time it receives any dose, whether the qualifying ear or not. A subject's treated ear will be classified into an actual treatment group based on the actual number of FX-322 doses received in that ear. An ear will be considered not treated up until the time it receives any dose, whether the qualifying ear or not. Untreated ears will be classified in the Placebo group up until the time it receives any dose, after which the ear will be classified into an actual treatment group based on the actual number of FX-322 doses received in that ear. Pre-dosing measurements will be mapped to treated or untreated based on dosing at Day 1. Subjects with treatment received in the non-qualified ear may contribute more than 1 treated ear to SfAS analyses. In the event that any subject/ear combination(s) receive 3 FX-322 doses, separate reports for subject/ear combination(s) receiving 3 FX-322 doses will be created, as applicable. Subject/ear combination(s) receiving 3 FX-322 doses will be included in the FX-322 total ears column.

For example, a subject treated with FX-322 2x in the qualified ear at Days 1 and 8 and treated with FX-322 2x in the not qualified ear at Days 15 and 21 will be summarized as follows:

- a. For summaries by subject: This subject will be included in the FX-322 4x section of the table.
- b. For summaries by ear:
  - i. The qualified ear data will be reported at all visits in the FX-322 2x section of the table in the Treated column.
  - ii. The not qualified ear data up to and including Day 15 will be reported in the Placebo section of the table in the Untreated column.
  - iii. The not qualified ear data after Day 15 will be reported at visits after Day 15 in the FX-322 2x section of the table in the Treated column.

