#### 4. ANALYSIS SAMPLES

The following definitions will be used to derive the analysis sets for this study.

- Full Analysis Set

The Full Analysis Set is defined as all randomized subjects who receive at least one dose of study drug (regardless of whether a full dose was administered) in the qualified ear per the

randomized treatment schedule. Subjects will be analyzed according to their randomized treatment group, as described in Section 3. For assessments completed by ear for each subject, treated (qualified) and untreated (not qualified) ears will be summarized separately, as described in Section 3. The FAS will be used to explore efficacy.

- Per Protocol Analysis Set

The Per Protocol Analysis Set is defined as subjects receiving all four doses of study drug or placebo in the qualified ear to be treated per the randomization treatment schedule and without major protocol deviations that could interfere with interpretation of the results. These major protocol deviations will be identified prior to breaking the study blind for the IA. Protocol deviations that occur after unblinding for the IA will be evaluated for major/minor classification by the blinded medical and study team prior to breaking the study blind for the CSR. If different from the FAS, the PPAS may be used in additional sensitivity analyses for efficacy. PPAS subjects will be analyzed according to their randomized treatment group, as described in Section 3. For assessments completed by ear for each subject, treated (qualified) and untreated (not qualified) ears will be summarized separately, as described in Section 3.

- Safety Analysis Set

The Safety Analysis Set will include all subjects exposed to study drug or placebo in any ear and will be analyzed according to the actual treatment group regardless of their randomized treatment assignment, as described in Section 3. For safety assessments by subject, the total number of FX-322 received in any ear will be used to assign actual treatment group. For safety assessments completed by ear for each subject, treated and untreated ears will be summarized separately, as described in Section 3. The SfAS will be used for the analysis of safety.

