## 8. SAFETY EVALUATION

### 8.1. Overview of Safety Analysis Methods

The assessment of local and systemic safety of single and repeated doses of FX-322 in subjects with stable sensorineural hearing loss is an objective of this study. The safety analyses will be performed for the safety analysis set and will include treatment-emergent adverse events (TEAEs), serious adverse events (SAEs), clinical laboratory measurements, vital signs, physical examination, otoscopic examination, tympanometry, concomitant medications, and Columbia-Suicide Severity Rating Scale (C-SSRS) assessments. Tabular summaries of descriptive statistics will be presented for all subjects included in the Safety Analysis Set and subjects will be classified into actual treatment groups based on the actual number of FX-322 doses received in any ear (qualified or not qualified).

Where appropriate, treated will be distinguished from the untreated ear, as described in Section 3. For unqualified ears that receive study treatment in error, the date and time of the study drug administration, or date if time is missing, or visit if date is missing (except for ear-related AEs, as provided below), will be used to identify assessments that will be classified as treated for safety analyses by ear.

If an assessment occurs on the same date that an unqualified ear receives study treatment in error, and assessment time or treatment start time is missing, the assessment will be presumed to have occurred prior to study drug administration for purposes of defining the ear as treated (i.e., the ear would be considered untreated at that assessment), with the exception of ear-related AEs, in which case the ear would be considered treated. The same logic would be applied to assessments other than ear-related AEs if the assessment occurred on the same visit that an unqualified ear receives study treatment in error and one or both dates are missing. For ear-related AEs, partial dates will be imputed for purposes of identifying treated ears in the same manner they are for purposes of defining TEAEs, as provided below.

For all safety endpoints, baseline will be the last non-missing value before first administration of study drug.

For all shift from baseline analyses, percentages will be based on the number of subjects in each baseline category.

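### Safety columns follow FX-322 doses eventually received, so events that stop dosing tend to leave the 4x column; no adverse-event table by randomised regimen is planned, and all untreated ears sit under Placebo

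*SAP*

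**What the plan says.** SAP Section 3 states that "all subjects in the SfAS will be classified into actual treatment groups based on the actual number of FX-322 doses received in any ear". Section 4 repeats that "the total number of FX-322 received in any ear will be used to assign actual treatment group", and Section 8.1 says the same. The columns are 0, 1, 2 and 4 doses. For anyone with three, "Subjects receiving 3 FX-322 doses will be included in the total column", with separate listings.

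By-ear tables work alike: "A subject's treated ear will be classified into an actual treatment group based on the actual number of FX-322 doses received in that ear". Three-dose ears get separate reports and enter a total column for FX-322 ears. An untreated ear belongs to Placebo until it receives any dose. In the worked example, data from the untreated ear of an FX-322 subject "will be reported in the Placebo section of the table in the Untreated column".

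The protocol lets an adverse event set the dose count:
- Section 9.1: "Discontinuation from FX-322 does not mean discontinuation from the study".
- Section 8.8.3, on a missed treatment: "that treatment will not be made up and subject will return for the next scheduled treatment".
- Section 13: after AESIs, the Medical Monitor, consulting the sponsor, decides whether remaining doses go ahead.

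Protocol 14.1.3 asks for safety analysis by actual treatment group. Protocol 14.1.7 adds pooled FX-322 and overall summaries. Protocol 14.1.7.5 asks for tympanometry and otoscopy by group and by treated or untreated ear.

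**The concern.** Local and systemic safety of single and repeat doses is a primary objective, and it will be read across the 1x, 2x and 4x columns. Under the SAP rule, column membership is a post-baseline variable that the safety outcome can change.

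The movement is one-way for the 4x regimen. A 4x subject who stops early moves down or loses a column. A 1x subject who stops after Day 1 stays in 1x, because the remaining injections are placebo. A 2x subject moves only if the Day 8 dose is not received. Events that do not stop dosing, or that first appear after Day 21, are unaffected.

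The by-ear tables raise a second issue. With every untreated ear under Placebo, the FX-322 groups lose their within-group untreated-ear comparison, and the Placebo untreated column is made up mostly of ears from subjects given FX-322.

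**Working it through.** **Inputs from the documents.** There are 24 subjects per group (4 × 24 = 96; 3 × 24 = 72). FX-322 is given on Day 1 (1x), Days 1 and 8 (2x), or Days 1, 8, 15 and 21 (4x), and every other injection is placebo. Otoscopy precedes each injection. During dosing, scheduled audiometry and word recognition (WR) occur only on Day 15, before the third injection, and next at Day 60 (Protocol 8.1.2, 10.1.3). The plan gives no event or stopping rate, so it has no figure to reproduce.

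**Step 1: counts only.** Suppose one 4x subject stops for an event after each of doses 1, 2 and 3. By regimen, 4x shows 3/24 = 12.5%. Under the SAP rule, 4x shows 0/21, 1x and 2x each gain one and show 1/25, and the three FX-322 columns hold 21 + 25 + 25 = 71 of 72 subjects. For events that stop dosing before dose 4, the 4x rate is zero by construction.

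**Step 2: any event, stopping possible after any injection.** Assumptions: event risk rA = 5% per FX-322 injection, rP per placebo injection, and a share f of events stops all later injections. By regimen with a FX-322 injections, the rate is 1 − (1−rA)^a (1−rP)^(4−a). Every subject who moves has had an event, so each column's event-free subjects are those of its own regimen. With s = rA·f, and Q1 and Q2 the event-free probabilities in 1x and 2x, the displayed rates are:
- 4x: 1 − 0.95^4/(1−s)^3
- 2x: 1 − Q2/(1−s²)
- 1x: 1 − Q1/(1+2s)

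Example with rP = 0 and f = 25%: s = 0.0125. 4x is 1 − 0.8145/0.9630 = 15.4%. 2x is 1 − 0.9025/0.9998 = 9.7%. 1x is 1 − 0.95/1.025 = 7.3%.

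Displayed 1x/2x/4x, in %:

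| f | rP = 0 | rP = 2.5% | rP = 5% (purely procedural) |
|---|---|---|---|
| 0 (as by regimen) | 5.0/9.8/18.5 | 11.9/14.2/18.5 | 18.5/18.5/18.5 |
| 10% | 5.9/9.7/17.3 | 12.8/14.2/17.3 | 19.4/18.5/17.3 |
| 25% | 7.3/9.7/15.4 | 14.1/14.2/15.4 | 20.5/18.5/15.4 |
| 50% | 9.5/9.7/12.1 | 16.1/14.2/12.1 | 22.4/18.5/12.1 |

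The 4x change is −1.2, −3.1 and −6.4 points at f = 10%, 25% and 50%.

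**Step 3: stopping at Day 15 only**, the case for AESIs found by scheduled audiometry or WR. A stopped 4x subject has had two doses and moves to 2x. With rP = 0, the chance of an event by then is 1 − 0.95² = 0.0975, and f is the share of these events that stops dosing. 4x is 1 − 0.8145/(1 − 0.0975f) = 17.7%, 16.5% and 14.4%. 2x is 1 − 0.9025/(1 + 0.0975f) = 10.6%, 11.9% and 13.9%. 1x stays at 5.0%.

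**Step 4: untreated ears.** With one untreated ear per subject and no wrong-ear injection, SAP 3 gives Placebo/1x/2x/4x = 96/0/0/0, of which 72 come from FX-322 subjects. Grouping by the subject's own arm gives 24/24/24/24. SAP 8.3 takes untreated-ear percentages over untreated ears in each group, so the FX-322 denominators would be zero. SAP 8.6.3 and 8.6.4 likewise plan untreated-ear shifts for each group.

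**Step 5: what is tabulated by randomised group.** This covers disposition, including study discontinuation for an adverse event (SAP 5.1), doses received (8.2), and the Full Analysis Set efficacy tables. The last include WR reductions on the Thornton-Raffin limits (7.3.9), thresholds by frequency (7.5.1) and PTA category shifts (7.5.5). Adverse events, AESIs, otoscopy and tympanometry are not included. SAP 8.4 tabulates events leading to study withdrawal, which Protocol 9.1 separates from stopping FX-322. The action taken with study drug is recorded in the eCRF (Protocol 13) but feeds no table described in the SAP.

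**The case against.** Analysis by actual treatment is the protocol's own choice, safety is descriptive, and no event is lost. Three-dose subjects stay in the total column and in listings, and three-dose ears get their own reports. That stands, and it is why the dose-count tables should remain.

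The shifts are also small against sampling noise. The standard error of 18.5% in 24 subjects is √(0.185 × 0.815/24), about 7.9 points. Tracing a handful of moved subjects through the exposure tables and the AE listings may be feasible. Table and listing specifications are held outside the SAP, so the listings may show more than can be seen here. This limits the size of the point. It does not supply a regimen-based table, and a systematic shift adds to noise rather than being excused by it.

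A reader might infer that the rule will make more doses look safer. The documents do not support that. They give no rates. With 10% of events stopping dosing, even purely procedural risk gives 19.4/18.5/17.3%, a spread of about half a subject in 24. For AESIs found at the scheduled Day 15 tests, 2x gains rather than 1x, so no steadily falling pattern follows.

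On ears, SAP 8.3, 8.6.3 and 8.6.4 refer back to Section 3, which can be read as governing. The adverse-event summary for both ears, counted by group, remains, and the efficacy tables show untreated-ear WR and thresholds by randomised group. The conflict with Protocol 14.1.7.5 is still there.

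**Conclusion.** The point holds, in three parts of unequal weight.

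1. Safety columns depend on doses eventually received. The 4x column tends to understate events that stop dosing and lower columns tend to overstate them; which one gains depends on timing. Events or otoscopy findings at an injection visit can move a 4x subject to 1x, 2x or three doses. Scheduled audiometric and WR AESIs move 4x subjects to 2x. At the assumed 5% per FX-322 injection, the loss in 4x is 1.2 to 6.4 points for stopping shares of 10% to 50% after any injection, and 0.8 to 4.1 points with Day 15 stopping only (18.5% to 17.7% and 14.4%). A rising pattern is flattened or reversed only if a substantial share of events stops dosing: about half with no placebo-injection risk, about a quarter with placebo risk at half the FX-322 risk. These rates are assumptions.

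2. The placement of untreated ears contradicts Protocol 14.1.7.5 and sits badly with SAP 8.3, 8.6.3 and 8.6.4. This needs no assumed rate.

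3. Minor: Protocol 14.1.7 promises a pooled FX-322 column. SAP 3 names none for by-subject safety tables, and SAP 11 does not list the change. A reader might infer that the column has been dropped. The SAP does not say so, and its total column most naturally means overall.

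**What to change.** - Keep the dose-count tables. Beside them, add AE, AESI, otoscopy and tympanometry tables by randomised regimen for the Safety Analysis Set, with three-dose subjects in their regimen's column and dosing errors footnoted.
- Add one table, by randomised regimen, of treatment-emergent events whose recorded action was interruption or withdrawal of study drug.
- Show untreated ears, until any wrong-ear injection, under the subject's own group, and reconcile SAP 3 with SAP 8.3, 8.6.3 and 8.6.4 and Protocol 14.1.7.5.
- Include the pooled FX-322 column in by-subject safety tables, or list its omission in SAP 11.

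The cost is SAP wording and programming, since all the data, including action taken, are already collected. The drawbacks are extra tables, and early stoppers shown under a regimen they did not fully receive; the retained dose-count tables cover that view. No dosing or clinical rule changes.

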#### 4. ANALYSIS SAMPLES

The following definitions will be used to derive the analysis sets for this study.

- Full Analysis Set

The Full Analysis Set is defined as all randomized subjects who receive at least one dose of study drug (regardless of whether a full dose was administered) in the qualified ear per the

randomized treatment schedule. Subjects will be analyzed according to their randomized treatment group, as described in Section 3. For assessments completed by ear for each subject, treated (qualified) and untreated (not qualified) ears will be summarized separately, as described in Section 3. The FAS will be used to explore efficacy.

- Per Protocol Analysis Set

The Per Protocol Analysis Set is defined as subjects receiving all four doses of study drug or placebo in the qualified ear to be treated per the randomization treatment schedule and without major protocol deviations that could interfere with interpretation of the results. These major protocol deviations will be identified prior to breaking the study blind for the IA. Protocol deviations that occur after unblinding for the IA will be evaluated for major/minor classification by the blinded medical and study team prior to breaking the study blind for the CSR. If different from the FAS, the PPAS may be used in additional sensitivity analyses for efficacy. PPAS subjects will be analyzed according to their randomized treatment group, as described in Section 3. For assessments completed by ear for each subject, treated (qualified) and untreated (not qualified) ears will be summarized separately, as described in Section 3.

- Safety Analysis Set

The Safety Analysis Set will include all subjects exposed to study drug or placebo in any ear and will be analyzed according to the actual treatment group regardless of their randomized treatment assignment, as described in Section 3. For safety assessments by subject, the total number of FX-322 received in any ear will be used to assign actual treatment group. For safety assessments completed by ear for each subject, treated and untreated ears will be summarized separately, as described in Section 3. The SfAS will be used for the analysis of safety.

## 5. STUDY SUBJECTS

### 5.1. Disposition of Subjects

The disposition of all consented subjects will be summarized in tables by treatment group and overall per Section 3. Subjects who failed screening or were not randomized will only be included in the overall column. The following disposition information will be summarized:

- The number of subjects consented (signed Informed Consent).
- The number and percentage of subjects who failed screening and the reasons for failure (Did not meet criteria, Withdrew consent, Lost to follow-up, Other).
- The number of subjects not randomized versus randomized and the number and percentage of subjects for each randomization stratification factor (Etiology of

- hearing loss: Sudden sensorineural hearing loss (SSNHL), Noise-induced hearing loss (NIHL); Word Recognition Score at Screening:  $\geq 50\%$  correct,  $< 50\%$  correct).
- The number and percentage of subjects in each analysis set (FAS, PPAS, SfAS).
  - The number and percentage of subjects receiving study treatment at each treatment visit (Day 1, 8, 15, 21).
  - The number and percentage of subjects who completed the study through Visit 9 (Day 210).
  - The number and percentage of subjects who discontinued the study early and the reasons for withdrawal (Adverse Event, Death, Lack of Efficacy, Lost to Follow-up, Non-Compliance With Study Drug, Physician Decision, Pregnancy, Progressive Disease, Protocol Violation, Recovery, Study Terminated by Sponsor, Technical Problem, Withdrawal by Subject, Other).
  - The number and percentage of subjects who discontinued the study early for reasons related to COVID-19 (Subject has confirmed COVID-19, Subject decision, Site decision).

Percentages for the number of subjects who failed screening and the reasons for failure will be based on the number of subjects who signed informed consent. All other percentages will use the number of randomized subjects as the denominator. All rows will be summarized by randomized treatment group.

The number and percentage of subjects who attended each visit will be summarized by randomized treatment group for the FAS.

A Kaplan-Meier plot of time from the date of randomization to the date of study completion or early discontinuation will be provided by randomized treatment group for all subjects randomized. Subjects who completed the study will be censored at their study completion date. For the IA, ongoing subjects will be censored at their Day 90 date, if available, or the data snapshot date if the Day 90 date is not available.

Subject disposition data for all subjects randomized will also be listed. A separate listing of subjects who failed screening with the reason for screen failure will be provided.

A listing of all subjects affected by the COVID-19 pandemic (discontinued the study early, had remote visits performed, or missed visits for reasons related due to COVID-19) will be provided by site and subject to document how the subject's participation was impacted by COVID-19.

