## 10. INTERIM ANALYSIS AND DATA MONITORING

The blinded data will be continuously monitored for safety. Interventional level aggregated data monitoring will be conducted once all enrolled subjects have completed the Day 90 visit (Visit 5) or were early discontinuations. An interim analysis of all Day 90 data may be performed to assist in data interpretation or to understand patterns of missingness in real-

time or to monitor data integrity. The study will continue as planned to final analysis when all patients have completed their day 210 visit.

The planned interim analysis will include select tables and figures planned for the CSR, with subjects grouped into randomized or actual treatment groups based on unblinded treatment assignments. Datasets supporting the select tables and figures will also be provided along with the raw randomization codes. In the tables and figures, model results and descriptive statistics through Visit 5 (Day 90) will be presented, as appropriate. With the exception of the subject disposition summary and Kaplan-Meier plot of time from the date of randomization to the date of study completion or early discontinuation, all data after Day 90 will be excluded.

The following tables and figures planned for the CSR analyses are planned for the IA: Subject Disposition for Consented subjects (Section 5.1), Demographic and Baseline Characteristics for the FAS (Section 5.2), Subject Visit Accountability for the FAS (Section 5.1), WR, WIN, and Audiometry accountability (Section 7.1.6), Major Protocol Deviations for Randomized Subjects (Section 6.1), Study Treatment Exposure for the FAS (Section 8.2), Word Recognition in Quiet for the FAS and PPS excluding analyses by site or subgroup (Section 7.3), Words-In-Noise for the FAS and PPS excluding analyses by site or subgroup (Section 7.4), Pure Tone Audiometry analyses for the FAS and PPS (Section 7.5), Composite Endpoint for the FAS and PPS (Section 7.5.9), TFI for the FAS (Section 7.7), HHI for the FAS (Section 7.8), HSI for the FAS (Section 7.9), Adverse Events for the SfAS (Section 8.3), Otoscopic Examination for the SfAS (Section 8.6.3), Tympanometry for the SfAS (Section 8.6.4), C-SSRS for the SfAS (Section 8.6.5), and concomitant medications for the SfAS (Section 8.6.6). Phoneme analyses, WR and WIN analyses by site or subgroup, as well as any sensitivity analyses for the FAS due to study treatment administration in the not qualified ear are excluded from the IA.

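### The interim Kaplan-Meier retention curve is biased downward after the Day 90 visit, because ongoing subjects are censored there while later withdrawals still count as events

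*SAP*

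**What the plan says.** SAP Section 5.1 defines the display, which covers everyone randomized and is split by assigned group: "A Kaplan-Meier plot of time from the date of randomization to the date of study completion or early discontinuation will be provided". On completers it adds: "Subjects who completed the study will be censored at their study completion date". Early discontinuation is therefore the only event.

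The same section sets a separate rule for subjects still in the study at the interim: "For the IA, ongoing subjects will be censored at their Day 90 date, if available, or the data snapshot date". The second date is a fallback, used only when a subject lacks the first.

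SAP Section 10 removes later data from the interim outputs but names two exceptions: "With the exception of the subject disposition summary and Kaplan-Meier plot of time from the date of randomization". The plot is thus allowed to use data from after Day 90.

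SAP Sections 7.1.3 and 10 place the interim after all enrolled subjects have reached Day 90 or left early. Subjects enrolled early will have follow-up well beyond Day 90 by then. Section 10 gives as one purpose of the interim "to assist in data interpretation or to understand patterns of missingness".

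**The concern.** The Day 90 censoring rule in SAP Section 5.1 covers only ongoing subjects. A subject who withdrew between Day 90 and the snapshot is not ongoing, so the rule does not apply, and the exemption in Section 10 keeps the withdrawal on its actual date. Two subjects with the same follow-up to Day 150 are therefore handled differently: the one who stays leaves the risk set at Day 90, and the one who withdraws stays in it and counts as an event. Whether a subject is censored at Day 90 depends on what happened afterwards. That breaks the Kaplan-Meier requirement that censoring be uninformative, and it pushes the curve in one direction only, downward.

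The fallback adds a smaller inconsistency. An ongoing subject with no Day 90 date stays at risk to the snapshot, while one who attended Day 90 does not.

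Among the listed interim outputs, this is the only one that shows time to discontinuation by arm. With 24 subjects per arm, a single late withdrawal can produce a visible drop that looks like differential dropout.

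**Working it through.** The documents state no figure for this plot, no accrual length and no dropout rate, so there is nothing to reproduce. I applied the rule in two ways.

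**1. One arm, by hand.** Inputs: 24 subjects per arm (SAP Section 6.2). Assumed: 2 withdraw before Day 90, 1 withdraws on Day 120, and 21 are retained. Of these 21, c have completed at the snapshot and 21 − c are ongoing, each with a Day 90 date and each actually followed past Day 120.

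- Before Day 90, under either rule: S = 22/24 = 91.7%.
- At Day 120 under the SAP rule, only the c completers and the withdrawing subject are at risk: S = (22/24) × c/(c + 1).
- At Day 120 with ongoing subjects censored at the snapshot, 22 are at risk: S = (22/24) × (21/22) = 21/24 = 87.5%, whatever c is.

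| Completers c | Ongoing | SAP rule | Snapshot censoring |
|---|---|---|---|
| 0 | 21 | 0% | 87.5% |
| 3 | 18 | 68.8% | 87.5% |
| 6 | 15 | 78.6% | 87.5% |
| 11 | 10 | 84.0% | 87.5% |
| 16 | 5 | 86.3% | 87.5% |
| 21 | 0 | 87.5% | 87.5% |

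The error shrinks as completers accumulate and vanishes when nobody is ongoing. The curve can reach zero only when c = 0. Truncating everyone at Day 90 gives 91.7% at Day 90 and no later curve.

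**2. Simulation.** Assumed: 24 per arm, uniform entry, constant dropout giving 90% true retention at Day 210, snapshot 90 days after the end of accrual. With accrual of A days, the longest possible follow-up is A + 90 days, and the share of subjects entered early enough to reach Day 210 is (A − 120)/A.

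| Accrual A (days) | Longest follow-up | Share able to complete | SAP rule, Day 210 | Snapshot censoring | Bias (points) |
|---|---|---|---|---|---|
| 120 | 210 | 0% | 47% | 90% | −43 |
| 180 | 270 | 60/180 = 33% | 85% | 90% | −5 |
| 270 | 360 | 150/270 = 56% | 88% | 90% | −2 |
| 400 | 490 | 280/400 = 70% | 89% | 90% | −1 |

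At 120 days of accrual the curve reached zero in 50% of arms. With no completers and every ongoing subject censored at Day 90, any later withdrawal is enough to cause this.

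**3. Sensitivity to dropout.** With 5% dropout before Day 90 and 10% of the remainder between Day 90 and Day 210, true retention is 0.95 × 0.90 = 85.5%. The SAP rule gives 77.8% at 180 days of accrual and 83.6% at 365 days, biases of −7.7 and −1.9 points. Over all combinations tried (5% or 10% in each period), the bias is about −1 to −8 points for 180 to 365 days of accrual. Snapshot censoring stays within 0.5 points of the truth throughout.

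**4. Before Day 90.** Retention just before Day 90 was unbiased in every scenario (for example 95% against 95%). Since SAP Table 7-1 allows the Day 90 visit from Day 75 to Day 105, in practice the distortion can begin from about Day 75.

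**The case against.** The strongest case against acting is that little depends on this figure.

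- The interim concerns data through Day 90, and that part of the curve is sound.
- The disposition summary, also exempt from the cut, gives discontinuations by arm and reason with randomized subjects as the denominator. Visit attendance and accountability tables for the hearing tests are also planned. A reader who sees 1 of 24 discontinued would not believe a curve at zero.
- No test is attached to the plot, all p-values are descriptive (SAP Section 7.1.4), and the study continues to Day 210 regardless (SAP Section 10, protocol Section 14.1.6).
- Figure specifications are held in separate documents (SAP Section 1). They may limit the time axis or show numbers at risk.
- Protocol Section 8.4.1 expects all 96 subjects to complete. With no late withdrawals there is no bias.

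All of this stands as a limit on importance, but none of it makes the rule correct. Nothing in the SAP confines the plot to Day 90, and an express exemption from the Day 90 cut points the other way.

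A reader might infer that the risk set loses all retained subjects after Day 90. It does not: completers remain at risk to completion, and ongoing subjects without a Day 90 date remain to the snapshot. A reader might also take the 47% estimate or the fall to zero as typical. These arise when nobody has completed, and the documents give no reason to expect accrual as short as 120 days.

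**Conclusion.** The concern holds for the part of the interim retention curve after the Day 90 visit. Read together, SAP Sections 5.1 and 10 make censoring depend on not having withdrawn later, and the curve is biased downward whenever an arm has a late withdrawal while other followed subjects are still ongoing. The direction follows from the rule. The size rests on assumptions about accrual and dropout: about 1 to 5 points at Day 210 for 180 to 400 days of accrual with 10% dropout by Day 210, somewhat more if late dropout is heavier, and extreme only with no completers in the arm.

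The documents do not support inferring that the interim conclusions, the final retention plot or the efficacy results are compromised. The final plot has no ongoing subjects, the efficacy models do not use this curve, and no decision rule depends on it. Severity is low.

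**What to change.** Choose one of two changes.

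- In SAP Section 5.1, censor every ongoing subject at the snapshot or last-contact date, whether or not a Day 90 date exists. The exemption in Section 10 can then stay, and the plot uses all available follow-up.
- Alternatively, truncate everyone at Day 90, censoring completers and later withdrawals there as well, and remove the Kaplan-Meier plot from the exceptions in Section 10.

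Either removes the bias and makes the two sections consistent. The cost is about one sentence in the SAP (plus the deletion in Section 10 for the second option) and one line of programming. No new data are needed.
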